## **19. Investigative Centers/Minimum and Maximum Enrollment**

Up to fifteen centers will participate in the study. Centers are chosen based on experience with the Ekso device and having appropriate personnel to conduct and support research studies. Each center is expected to contribute at least 1 Run-in and 8 Randomized Participants and no center shall contribute more than 4 Run-ins and 37 Randomized Participants (30% of total maximum enrollment for the Randomized group). If very low enrolling centers (<8 Randomized Participants) exist after study close, these may be combined with other centers for analysis purposes assuming that all centers maintained adherence to the protocol and that the data gathering mechanism is the same for all centers.

## **20. Quality Assurance of the Data**

Participant case report forms will be collected and reviewed for completeness and accuracy by the Monitor as well as for any evidence suggesting Participant risk. Where discrepancies are noted, they will be resolved with the investigator and/or an individual designated by the investigator. Where the data are incomplete, attempts will be made to obtain the missing data. The Sponsor reserves the right to use a third-party data manager throughout the study period. The data manager will be required to have quality assurance procedures in place.

## **21. Study Termination**

The Sponsor reserves the right to terminate the study before enrollment has been completed and to report on study results at interim time-points without statistical penalty.

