## **17. Statistical Methods**

### **17.1 General Principles**

The primary analysis for all baseline characteristics and study outcomes will include all available data for all enrolled subjects. Standard summary statistics will be calculated for all study variables. For continuous variables, statistics will include means, standard deviations, medians and ranges. Categorical variables will be summarized in frequency distributions.

Statistical analyses will be conducted according to the principles of intent-to-treat, under which subjects will be evaluated according to their randomized assignment regardless of the treatment actually received. P-values for tests of superiority will be two-sided and for non-inferiority one-sided, with values less than 0.05 deemed statistically significant.

Statistical analyses will be conducted in SAS version 9.3 or above (SAS Institute, Cary, N.C.), R version 3.2 or above (R Foundation for Statistical Computing, Vienna, Austria, <http://www.R-project.org>) or another validated statistical software package.

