### **17.2 Primary Endpoint**

The primary endpoint is change in gait speed (self-selected and fast) demonstrated during the 10MWT after 12 weeks of training, compared to baseline. Two hypotheses are associated with this endpoint; first, that the mean change in the Ekso intervention group will be statistically superior to that in the passive control group, as follows:

$$\begin{aligned} H_0: \mu_E &\leq \mu_P \\ H_A: \mu_E &> \mu_P, \end{aligned}$$

where  $\mu_E$  and  $\mu_P$  are the mean change in the Ekso and passive control groups, respectively. The hypothesis will be tested using a two-sample Student's t or Wilcoxon rank-sum depending upon normality of the trial data.

The second hypothesis is that the mean change in the Ekso intervention group will be statistically non-inferior to that in the active control group, as follows:

$$\begin{aligned} H_0: \mu_E &\leq \mu_A - \Delta \\ H_A: \mu_E &> \mu_A - \Delta, \end{aligned}$$

where  $\mu_E$  and  $\mu_A$  are the mean change in the Ekso and active control groups, respectively, and  $\Delta$  is the non-inferiority margin.  $\Delta$  is selected based upon the principles that it should be substantially less than the expected effect size comparing Ekso to passive control, and that it should represent a clinically acceptable margin of effect when differentiating Ekso from active control.

For this purpose,  $\Delta$  is therefore defined to be 0.055 m/s, which is one-half of the hypothesized treatment effect of Ekso over passive control as stated below, and one-eighth of the threshold of 0.44 m/s (1.0 mph) commonly used to represent gait speed associated with community ambulation.

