### 17.4 Sample Size

Computations for sample size and power are based on effect sizes derived from internal study data and the relevant clinical literature for the primary endpoint. For the Ekso intervention group, the postulated effect (derived from internal study data) is a mean change from baseline in gait speed of 0.11 m/s, with a corresponding standard deviation of 0.18 m/s. For the active control group, the postulated effect is a mean change from baseline in gait speed of 0.078 m/s (derived from the relevant clinical literature), with a corresponding standard deviation of 0.108 m/s.

The passive control group is postulated to have a mean change of zero with the same standard deviation as active control, or 0.108 m/s. Sample size and power are then computed for both statistical tests cited above: superiority of Ekso to passive control and non-inferiority of Ekso to active control.

Under 2:2:1 randomization with a desired power of 80%, the required sample size for superiority of Ekso intervention to passive control is 38 subjects with evaluable data in the Ekso group and 19 in passive control (incorporating the 2:1 Ekso: passive control randomization). For non-inferiority of Ekso to active control, the groups are of equal size and the required sample size is 37 per group.

Taking the greater of these numbers for each randomized group, total sample size under 2:2:1 randomization is therefore 38 for Ekso intervention, 38 for active control and 19 for passive control, a total of 95. To account for possible attrition as well as potential variance from the postulated effects, up to 127 subjects in the randomized group will be enrolled.

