## **27. Publication**

Manuscripts, abstracts, posters, or other informational materials may be presented at scientific meetings, or published in professional journals. The Sponsor reserves the right to publish the results of the run-in group and/or primary endpoint analysis results on the minimum sample size needed in a single publication. Longer-term, qualitative and quantitative analysis may be reported in a separate publication. This study will be listed on clinical trials.gov. Therefore, results will be published per FDA requirements.

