### 1.3 Primary Endpoint

*Efficacy:* The primary endpoint is the mean increase in gait speed demonstrated during the 10MWT after 12 weeks/36 sessions of training compared to baseline and compared between groups. Both self-selected and fast speeds will be performed on the 10MWT, with the fast speed taking precedent.

Hypothesis #1: The mean change in the Ekso G intervention group will be statistically superior to that in the passive control group, as follows:

$$H_0: \mu_E \leq \mu_p \text{ vs } H_a: \mu_E > \mu_p$$

where  $\mu_E$  and  $\mu_p$  are the mean change in the Ekso G intervention group and the passive control group, respectively.

Hypothesis #2: Using the two one-sided (TOST) procedure, the null hypothesis of non-equivalence or non-inferiority of means will be tested for the Ekso GT ( $\mu_E$ ) versus the Active Control ( $\mu_A$ ) using a two-group design with equal sample sizes in the two groups. We want to demonstrate that the mean gait speeds will have similar distributions on the average for the two intervention groups. We specify that the practical difference in means is therefore defined to be 0.055 m/s, which is one-half of the hypothesized treatment effect of Ekso G over passive control as stated below, and one-eighth of the threshold of 0.44 m/s (1.0 mph) commonly used to represent gait speed associated with community ambulation. The two null hypotheses are specified below:

$$H_{01}: \mu_E - \mu_A \leq \delta_L \text{ or } H_{01}: \mu_E - \mu_A + \delta_U \leq 0 \text{ vs } H_{02}: \mu_E - \mu_A \geq \delta_L \text{ or } H_{02}: \mu_E - \mu_A - \delta_U \geq 0$$

The composite null hypothesis is that the two groups have unequal mean gait speeds. The alternative hypothesis is that the mean gait speeds are equivalent for both the Ekso G Intervention group and the active control group.

Reject  $H_{01}$  if the observed difference in the two means is too large. That is, reject if the lower bound for two-sided  $100(1-2\alpha)\%$  confidence interval for  $\mu_E - \mu_A$  is greater than the group mean multiplied by the assumed practical difference of 0.055 m/s.

Reject  $H_{02}$  if the observed difference in means is too small. That is, reject if the upper bound for the two-sided  $100(1-2\alpha)\%$  confidence interval for  $\mu_E - \mu_A$  is less than the group mean multiplied by the assumed practical difference of 0.055 m/s.

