#### **1.6 Multiplicity**

Although there is only one efficacy study endpoint and one safety study endpoint, the assessment of primary and secondary endpoints as well as the repeated measurement of the primary efficacy endpoint over time warrants the implementation of a conservative alpha allocation strategy. Common methods for handling endpoint multiplicity as suggested by Bonferroni and Tukey are useful adjustments for establishing significance levels and hypothesis testing (Hochberg et al). Moreover, a hierarchical test procedure (i.e., fixed sequence procedure) will be followed in order to reflect the relative clinical importance of the null hypothesis for the primary and secondary endpoints. The fixed sequence procedure tests hierarchically ordered hypothesis in sequence until at a 0.05 significance level until first non-rejection. Once a hypothesis is not rejected, no further testing will be performed. It is assumed that

the overall study hypothesis is more important than the primary and secondary endpoint hypotheses and the primary endpoint hypotheses are more important than the secondary endpoint hypotheses.

All analysis will be performed using SAS Analytics Pro, Version 9.3 and JMP Statistical Software, Version 13.2 (SAS Institute Inc., Cary, NC or MedCalc Statistics for Biomedical Research, Version 18.1, MedCalc Software, Belgium, EU.

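### Protocol section 21 waives adjustment for interim reporting and no analysis is named as confirmatory; testing at 95 evaluable and again at the end would put the one-sided non-inferiority error at 5.0% to 7.1% instead of 5%

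*Protocol*

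**What the plan says.** Protocol section 21 reserves the sponsor's right to end the study before enrolment is complete and "to report on study results at interim time-points without statistical penalty". It does not say how many interim reports there may be, when they may occur, or whether they may contain comparative tests.

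Protocol section 27 allows publication of "primary endpoint analysis results on the minimum sample size needed in a single publication". Section 17.4 fixes that minimum as "38 for Ekso intervention, 38 for active control and 19 for passive control, a total of 95" evaluable, and then says that "up to 127 subjects in the randomized group will be enrolled", to cover attrition and departures from the assumed effects. Section 27 contains no waiver of its own.

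The significance rule is in protocol section 17.1: "P-values for tests of superiority will be two-sided and for non-inferiority one-sided, with values less than 0.05 deemed statistically significant". For superiority, section 17.2 names Student's t or "Wilcoxon rank-sum depending upon normality of the trial data". SAP section 1.3 treats the comparison of Ekso with active control differently: "Using the two one-sided (TOST) procedure, the null hypothesis of non-equivalence or non-inferiority of means will be tested".

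SAP section 1.6 says that "the repeated measurement of the primary efficacy endpoint over time warrants the implementation of a conservative alpha allocation strategy" and sets a fixed sequence across hypotheses. It says nothing about repeating a test as participants accumulate. The data safety monitoring board in protocol section 12 is described only as adjudicating serious adverse events and protocol violations.

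**The concern.** A statistical penalty, in ordinary usage, is the adjustment that keeps the error rate at its stated level when the same hypothesis is tested more than once on growing data. Section 21 sets that adjustment aside in advance. Sections 27 and 17.4 then identify a concrete early point, 95 evaluable, at which primary results may be published while up to 127 may be enrolled. No passage says whether the analysis at that point or a later one decides the trial.

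If both are run and either may carry the claim, a chance finding has two opportunities to reach p<0.05. A reader of the eventual publication could not tell whether the stated 5% level applied. The hypothesis most exposed is non-inferiority to standard gait training, one of the protocol's two primary hypotheses.

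**Working it through.** **Inputs.** Protocol 17.4: Ekso change 0.11 m/s, SD 0.18; active control 0.078, SD 0.108; passive control 0, SD 0.108; 38/38/19 evaluable (Ekso/active/passive); up to 127 randomised. Protocol 17.2: margin 0.055 m/s. Protocol 17.1: superiority two-sided 0.05, non-inferiority one-sided 0.05. The documents give neither attrition nor a number of looks. I assume one look at 95 evaluable and one at a final number n between 95 and 127.

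**Reproducing the plan's sample size** (unequal-variance t):

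- Superiority, 38 vs 19: SE = √(0.18²/38 + 0.108²/19) = 0.0383; 0.11/0.0383 = 2.87; two-sided 0.05 gives 80.5% power.
- Non-inferiority, 37 per group: SE = √((0.18² + 0.108²)/37) = 0.0345; (0.11 − 0.078 + 0.055)/0.0345 = 2.52; one-sided 0.05 gives 80.2% power.

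The figure of 95 is reproduced, at the significance levels in section 17.1.

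**Two unadjusted looks, normal theory.** The two test statistics are bivariate normal with correlation ρ = √(95/n). The non-inferiority error is 1 − P(Z₁<1.645, Z₂<1.645). The two-sided superiority error is 1 − P(|Z₁|<1.960, |Z₂|<1.960). Attrition is 1 − n/127.

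| Final evaluable n | Attrition from 127 | ρ | Non-inferiority, one-sided | Superiority, two-sided | of which in Ekso's favour |
|---|---|---|---|---|---|
| 95 (looks coincide) | 25.2% | 1 | 5.0% | 5.0% | 2.5% |
| 102 | 19.7% | 0.965 | 6.1% | 6.2% | 3.1% |
| 108 | 15.0% | 0.938 | 6.4% | 6.6% | 3.3% |
| 114 | 10.2% | 0.913 | 6.7% | 6.9% | 3.5% |
| 127 | 0% | 0.865 | 7.1% | 7.3% | 3.7% |

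**Simulation with the planned SDs**, first look 38/38/19, final 51/51/25 (400,000 trials per case; Wilcoxon 200,000):

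| Test | One look at 95 | Looks at 95 and 127 |
|---|---|---|
| Non-inferiority, pooled t, true difference −0.055 | 5.0% | 7.2% |
| Superiority, Welch, two-sided | 5.0% | 7.4% |
| Superiority, pooled Student's t, two-sided | 2.2% | 3.4% |
| Superiority, Wilcoxon, two-sided | 3.5% | 5.3% |
| SAP TOST, 90% CI within ±0.055, true difference −0.055 | 0.9% | 3.7% |

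The pooled t-test for superiority is conservative because the larger group has the larger SD. The pooled SD is √((37×0.18² + 18×0.108²)/55) = 0.160, so the pooled SE is 0.160 × √(1/38 + 1/19) = 0.0450, against a true 0.0383. With equal SDs this protection disappears; Wilcoxon with equal SDs reaches 7.3% at 127.

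TOST is low because at 38 per group the expected 90% interval half-width is about 1.666 × √(0.044064/38) = 0.057, wider than the margin, so equivalence can rarely be declared.

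**The case against.** The strongest reply is that no passage schedules a test at 95 and another at the end. Section 27 fits a single primary analysis, and its next sentence reserves longer-term analyses for a separate publication, which suggests that primary testing might end there. The protocol also uses time point for assessment visits (section 3 and Table 4), and SAP 1.4 reports success at 6, 12 and 24 weeks. If section 21 means visits, SAP 1.6 already speaks to repeated measurement. Further, 7.1% requires all 127 to be evaluable, although 127 was chosen partly to absorb attrition; at 15% to 20% attrition the figure is 6.1% to 6.4%. Finally, several tests named in the documents stay under 5%, and the SAP's fixed sequence, which puts the overall study hypothesis first, could lower the realised error further.

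Much of this stands. The inflation is conditional, 7.1% is the zero-attrition ceiling for one extra look at 95, and the effect of the fixed sequence is not quantified here. It does not remove the problem. Section 27 does not say that testing ends at 95. The interim phrase in section 21 shares a sentence with stopping before enrolment is complete, so a reading in terms of accumulating data is at least as natural. The protocol's one-sided non-inferiority test has no conservative cushion. Section 21 also caps neither the number nor the timing of looks: a third look, at 48, 95 and 127, would give 9.8%.

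**Conclusion.** The concern holds and should be fixed. The plan expressly waives adjustment for interim reporting, names no confirmatory analysis, and contains no boundary for repeated tests on accumulating participants. If the primary tests are run at 95 evaluable and again at the end, with success at either, the protocol's one-sided non-inferiority error is 5.0% to 7.1%. Superiority tested at an accurate nominal level is 5.0% to 7.3% two-sided, or 2.5% to 3.7% in Ekso's favour.

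With the planned SDs, superiority by pooled t stays at 2.2% to 3.4%, Wilcoxon at 3.5% to about 5.3%, and the SAP's TOST at 0.9% to 3.7%. The ranges rest on an assumed second look and on a final evaluable number that the documents do not give. The inflation is modest; the defect is that the text permits it and disclaims the correction.

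**What to change.** **Preferred.** Delete the waiver in section 21. State in the protocol and the SAP that the between-group primary tests are done once, after the last randomised participant's week-12 evaluation. Limit earlier reports to run-in or non-comparative data, and align section 27. Stopping for reasons unrelated to results can remain without adjustment if the text says so. This takes one or two sentences in each place and costs no power; the sponsor gives up only unadjusted early comparative reporting.

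**If an early look is wanted.** Pre-specify one at 95 evaluable with a named spending function, for example the Lan-DeMets O'Brien-Fleming type. Fix the planned maximum evaluable number beforehand, and allow a primary claim at the look only for a test whose boundary is crossed. Illustrative boundaries:

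| Maximum evaluable | Superiority, two-sided p (look, then final) | Non-inferiority, one-sided p (look, then final) |
|---|---|---|
| 127 | 0.0191, then 0.0443 | 0.0234, then 0.0432 |
| 102 | 0.0404, then 0.0394 | 0.0423, then 0.0392 |

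Compared with a single final test at the planned effects (normal approximation, unpooled variance), overall power falls by under one point. Superiority goes from 91.2% to 90.8% with 127 evaluable and from 84.3% to about 83.7% with 102. Non-inferiority goes from 90.6% to 90.0% and from 84.4% to about 83.5%.

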## **22. Personnel Responsibilities**

### **22.1 Principal investigator responsibilities**

- a)** Permit monitor inspection of facilities and records.
- b)** Permit inspection of facilities and records by government bodies.
- c)** Submit protocol and informed consent to IRB and await approval.
- d)** Submit proposed amendments to protocol and informed consent to IRB and await approval, unless the change reduces the risk to Participants.
- e)** Obtain informed consent of Participants.
- f)** Implement study in accordance with protocol.
- g)** Complete source documents and case report forms.
- h)** Explain deviations from protocol and report to monitor.
- i)** Submit annual progress reports, final reports, and adverse effect reports to IRB and sponsor as required by law.
- j)** Maintain medical histories of Participants.
- k)** Retain records for two years following study completion.

## **22.2      Sponsor Responsibilities**

Listed below are the Sponsor's responsibilities for this study.

- a)**      Assure IRB approval of protocol and informed consent is obtained
- b)**      Select and train monitors
- c)**      Select investigators
- d)**      Train site personnel in device use (as appropriate)
- e)**      Obtain protocol signature, curriculum vitae and proof of appropriate licensure of investigator and other study staff
- f)**      Investigate device-related adverse events
- g)**      Oversight responsibility for data review and analysis
- h)**      Obtain statement of financial disclosure for publication and presentation purposes

## **23.      Potential Risks to Study Participants and Mitigation of Risks**

- 1) The risk of falling: Having experienced therapists conduct the training sessions will minimize the risk of falling.
- 2) Risk of exceeding range of motion: This would be caused if any device moves the Participant beyond the normal range of motion, resulting in a strain, sprain or fracture. For the Ekso device, this risk is lessened by mechanical hard stops that prevent the device from exceeding a normal human range of motion even in the event of an electrical or software failure. Software systems are also in place to further reduce range of motion to improve fit and comfort during walking. Participants will be evaluated by clinicians who will eliminate Participants from being included in the study if Participants cannot meet the required range of motion. For all other devices, this risk will be mitigated through proper settings by the physical therapist in charge of Participants treatment.
- 3) Discomfort, skin pressure/friction, bruising, pain, or unusual swelling caused by any device that contacts the skin. This risk will be minimized by a thorough skin check performed by experienced personnel at each training session. Adjustments to the harness placement and additional padding will be assessed to decrease the risk of skin breakdown as well.
- 4) Blood pressure instability related to standing or activity. This risk will be reduced by checking blood pressure and heart rate prior to training, and as necessary during training and after.
- 5) Reflex bowel or bladder activity or autonomic instability during walking. This risk will be minimized by requiring Participants to relieve bowels and bladder prior to walking.
- 6) Spasms triggered by joint movement in the device. This risk will be reduced through screening prior to enrollment in the study. Participants cannot take part if the Participant's muscles are too stiff.
- 7) Any device used during this study could malfunction. In the event of device malfunction, Participants will be able to safely transfer out of the device.
- 8) There is a risk of fractures when participating in a therapy program: this will be minimized by requiring medical clearance if Participants are at risk for severe osteoporosis.
- 9) Risk from loss of confidentiality. To minimize this risk, Participants will be assigned a unique numeric identifier to be included on test records and test documentation. Research information shared with people outside the study center will not include Participants' name, address, telephone number or any other direct personal identifier unless disclosure of the personal identifier is required by law. Records may be viewed by the study sponsor and Investigators, study monitors and auditors (such as the IRB) who make sure that the study is being done properly.

10) Muscle strains and tendon sprains and swelling due to joint misalignment during stepping. To minimize this risk, therapists and trainers will have undergone training to protect joints. The Ekso minimizes this risk by allowing movement of the hip, knee, and ankle only in the sagittal plane. BWSTT reduces this risk by providing body weight support during stepping.

